7.8. Efficacy Analyses

For any efficacy assessment that is taken on 2 consecutive days within a visit (ie, 6MWT, NSAA items and total score, FVC % predicted), the average value will be used. If the assessment is taken or available only on 1 day, then the value on that day will be used. A value that is marked as invalid or not completed successfully on the eCRF will be considered a missing value.

Analyses of the primary and secondary efficacy endpoints will be performed separately on the primary efficacy set, the efficacy set, and the subset of patients with Baseline 6MWT distance >450 meters.

Due to the high dropout rate in the untreated group, comparisons between the eteplirsen-treated group and the untreated control group will not be meaningful. Therefore, only summaries by treatment group will be presented.

7.8.1 Analyses of Primary Efficacy Endpoint

Missing 6MWT values will be imputed as specified in Section 6.2.1.

The primary efficacy endpoint, change from baseline at Week 96 in 6MWT distance, will be summarized as part of the by-visit summary for 6MWT.

Observed 6MWT distance and change from baseline will be summarized by treatment group and visit using descriptive statistics. A plot of the mean (+/- SE) of change from baseline in 6MWT distance will be generated.

In addition, summaries by Baseline 6MWT and Baseline age subgroups (see Section 6.5) may be presented for the primary efficacy set.

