13.9.2. Analyses of Primary Efficacy Endpoint

The analysis of change from Baseline to Week 96 (the primary time point of interest) in the 6MWT will be based on a mixed model repeated measures (MMRM) analysis, with treatment group, time, time by treatment group interaction, Baseline 6MWT distance, and Baseline 6MWT distance by time interaction as fixed effects; and patient as a random effect. Additional baseline variables may be added as covariates in the SAP. A heterogeneous autoregressive (1) variance-covariance matrix will be used. Estimates for changes from Baseline at each time point in each treatment group and for treatment differences will be provided with 95% confidence intervals and descriptive p-values using appropriate contrasts from the model. Due to the potential difference in progression based on DMD genotype in the control group, notably those with deletions amenable to skipping exon 44, additional sensitivity analyses may be performed.

If there is strong evidence suggesting that data for any of these endpoints deviate from normal distribution, then an analysis of covariance (ANCOVA) for ranked data (Stokes 2000) will be utilized.

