4.4.2 Final Analysis

A final analysis of safety and efficacy will be conducted once the last patient completes the entire study and the resulting database is cleaned, quality assured, locked, and unblinded. All statistical analyses will be performed by or under the supervision of the Sponsor. All available data will be included in data listings and tabulations. Due to the small population size and large dropout rate of the untreated control group, only descriptive summaries will be presented. An external control dataset will be identified and used to evaluate the effect of eteplirsen treatment. The statistical methods for the identification and use of the external control dataset will be presented in a supplemental SAP.

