6.2. Handling of Missing Data

6.2.1 Imputation of Missing Values

6WMT distance

If the patient is confirmed to have LOA (section 6.7), a value of 0 (zero) meters will be imputed for any missing values at the time or after the confirmation of LOA.

CCI

NSAA item and total score

If 4 or fewer of 17 NSAA items are missing, the score for the missing items will be assigned a value of zero. The NSAA total score will be calculated as the sum of the scores for the completed items. The total NSAA score will be treated as missing values when 5 or more items are missing.

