8. CHANGES IN PLANNED ANALYSES

8.1. Changes from Protocol-Planned Analyses

The following changes were made compared to the protocol-planned analyses:

- Comparisons between the eteplirsen-treated group and the untreated control group will not be performed due to the expected very small number of patients in the untreated control group and the differences in the populations between the treated and untreated groups. No hypothesis test, no p-value and no inferential statistics will be made for comparison of eteplirsen treated patients and untreated patients
- CCI [REDACTED]
- The observed values and changes from baseline for clinical laboratory assessments, vital signs and ECG will only be summarized for baseline, the last visit (final observation) and the highest/lowest values. All clinical laboratory assessments, vital signs and ECG results by visit will be in data listing.
- Renamed “predefined change abnormal” to “predefined markedly abnormal” for clinical laboratory tests and other safety endpoints.
- CCI [REDACTED]

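### SAP 7.8.1 replaces the protocol's per-arm MMRM estimate of Week 96 6MWT change with descriptive means, and no readable reason covers the treated arm

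*SAP*

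**What the plan says.** **Protocol 13.9.2** plans an MMRM for 6MWT change with group, visit, group by visit, Baseline 6MWT and Baseline by visit, plus a patient effect. Its output is per arm as well as comparative: "Estimates for changes from Baseline at each time point in each treatment group and for treatment differences will be provided with 95% confidence intervals". On covariance: "A heterogeneous autoregressive (1) variance-covariance matrix will be used".

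**SAP 7.8.1** has no model: "Observed 6MWT distance and change from baseline will be summarized by treatment group and visit using descriptive statistics". It adds a plot of mean ± SE. SAP 6.1 defines the descriptive statistics as n, mean, SD, median, minimum and maximum, so no confidence interval is reported.

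**Missing walks.** SAP 7.8.1 applies SAP 6.2.1, under which, once LOA is confirmed, "a value of 0 (zero) meters will be imputed for any missing values at the time or after the confirmation of LOA". No other 6MWT rule is readable; a redacted block follows it.

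**Reasons given.**
- SAP 4.4.2: "Due to the small population size and large dropout rate of the untreated control group, only descriptive summaries will be presented".
- SAP 7.8: "Due to the high dropout rate in the untreated group, comparisons between the eteplirsen-treated group and the untreated control group will not be meaningful".
- SAP 8.1 cites the very small untreated group and population differences, then states: "No hypothesis test, no p-value and no inferential statistics will be made for comparison of eteplirsen treated patients and untreated patients". Two of its other bullets are redacted.

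**Where the effect is evaluated.** SAP 4.4.2 also says: "An external control dataset will be identified and used to evaluate the effect of eteplirsen treatment". The methods are left to a supplemental SAP, which is not among the documents.

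**Visit assignment.** SAP 6.6 assigns values to visits by eCRF page. The protocol schedules use one joint column for Week 96 and early termination, with the same assessments.

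**The concern.** The protocol promised two things: an estimate within each arm and a difference between arms. The SAP gives reasons for dropping the second, and both have gone. A within-arm estimate in the treated group does not need the untreated group, so that group's size, dropout or genotype does not explain its removal. Protocol 13.1 says departures from its planned analyses will be recorded in the SAP, and no readable bullet in SAP 8.1 records this one.

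The SAP keeps within-arm inference elsewhere: 95% CIs for Kaplan-Meier medians (7.8.2) and a one-sample permutation test for dystrophin (7.8.4). The primary endpoint therefore gets less than some secondary endpoints.

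At stake is the only readable report of the primary endpoint in this SAP. The mean of patients who remain is open to selective loss. A confidence interval that a reader builds from n and SD is centred on the same shifted mean.

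**Working it through.** The readable text gives no power or precision figure for this endpoint, so there is none to reproduce. The planned numbers add up: 70 + 20 + 10 + 10 = 110.

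**1. What was dropped, and which reason reaches it**

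| Output in Protocol 13.9.2 | In the SAP? | Readable reason |
|---|---|---|
| Between-arm difference, CI, p-value | No | Yes: 4.4.2, 7.8, 8.1 |
| Untreated-arm estimate with CI | No | Yes: 4.4.2 (size, dropout) |
| Treated-arm estimate with CI | No | None found |

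**2. How bias arises.** Let f be the fraction with no Week 96 value, counting LOA zeros as values. Then

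observed mean − full mean = f × (mean of those with a value − mean of those without).

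At f = 0.10, a bias of 5 to 12 m needs the two groups to differ by 50 to 120 m. At f = 0.30, a bias of 17 to 38 m needs 57 to 127 m. If dropout is unrelated to decline, the difference and the bias are zero.

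**3. Size under assumed selective dropout.** Dropout rates and mechanisms are assumptions. Decline and SD come from Protocol 13.2 (42.3 m/year with SD 73.9; 57 m/year with SD 104; about 60 m in 48 weeks). All set-ups keep LOA zeros and let dropout depend on earlier observed change.

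| Set-up | Bias of descriptive mean |
|---|---|
| A: n = 70, Week 96 SD 104 m, adjacent-visit correlation 0.9 | about +5 m at 10% missing; +24 to +25 m at 27% (strong dependence); about 0 if random |
| B: random slopes, SD 74 m/year, 25 m visit noise, odds ratio 1.5 to 2 per 50 m | 5 to 9 m at 10%; at 30%, +17 to +29 m if fast decliners leave and −17 to −26 m if better walkers leave; under 2 m if random |
| C: n = 70 fitted alone, SD 74 m/year | 7 to 12 m at 10%; 23 to 38 m at 30% |

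The range of 5 to 12 m and 17 to 38 m spans these. It is sensitive to the SD: set-up B with 104 m/year gives 29 to 51 m at 30%.

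**4. Set against precision.** Half-width = 1.96 × SD/√n, with the one-year SDs 73.9 and 104 m:
- n = 70: 17.3 and 24.4 m
- n = 63 (10% missing): 18.2 and 25.7 m
- n = 49 (30% missing): 20.7 and 29.1 m

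The Week 96 SD is not stated and may be larger. In set-up B the half-width at 30% missing was 35 to 36 m, and the raw interval covered the full-data mean 62 to 85% of the time. There the bias is 17/36 = 0.5 to 29/35 = 0.8 of the half-width.

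**5. Does a model recover it?** When dropout depends only on observed values (MAR), the likelihood estimate was within 0.6 m of the full-data mean in A. In C, with unrestricted covariance, its bias was about 1 m or less, and its RMSE was no worse than that of the raw mean even under random dropout. Forcing the protocol's heterogeneous AR(1) in B left 6 to 11 m and 83 to 91% coverage at 30% missing. The covariance choice therefore matters.

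**6. Early-termination walks, if tabulated as Week 96.** With linear decline, shift = f × rate × (96 − t). For f = 0.10:
- t = 29: 0.10 × (42.3/52) × 67 = 5.5 m, up to 0.10 × (60/48) × 67 = 8.4 m
- t = 77: 1.5 to 2.4 m

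Under selective dropout these walks can offset or add to the bias. In set-up A they moved it from +24.7 to +12.8 m in one case and from +10.2 to +13.0 m in another.

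**The case against.** The strongest reply has four parts.

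- **Redaction and the supplemental SAP.** SAP 8.1 has redacted bullets, and the treatment effect is moved to a document not seen here, which may contain a modelled treated-arm estimate. This stands. The claim is only that no readable reason covers the treated arm.
- **The per-arm figures came from a two-group model that was openly dropped.** This is true of the protocol's model, but the treated arm can be fitted on its own.
- **High dropout is documented only for the untreated arm.** This stands. The 30% figure for treated patients is an assumption, and at 10% the bias is 5 to 12 m.
- **A reader can form a CI from n and SD, and SAP 7.8.2 reports LOA counts.** This also stands in part. The main loss is the MAR-based estimate rather than the interval. The by-visit n still mixes walked distances with imputed zeros.

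A reader might infer three stronger things that the documents do not support:

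- **That 7.8.1 is a plain observed-case analysis.** It is not: confirmed LOA enters as 0 m, which removes the most obvious informative loss.
- **That the table will understate decline.** The direction depends on who leaves, and nothing in the documents settles that.
- **That early-termination walks do enter the Week 96 row.** This depends on the eCRF, which is not available. Identical assessments describe visit content, not the page label. SAP 7.1 counts Week 96 completers separately from early discontinuations, and SAP 6.7 separates early withdrawal from Week 96.

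**Conclusion.** The point holds in limited form. SAP 7.8.1 removes a planned within-arm estimate of the primary endpoint, and the readable reasons justify removing only the comparison and, through the untreated arm's size and dropout, that arm's estimate. The consequence is conditional: roughly 5 to 12 m at 10% missing and 17 to 38 m at 30% in the treated arm, in either direction, and near zero if dropout is random. These sizes rest on assumed dropout rates, dropout mechanisms and Week 96 variability.

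The early-termination point is a request for clarification. It matters only if the eCRF records early termination on the Week 96 page.

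This is a worthwhile, low-cost improvement with medium confidence. It does not show that the plan's reported mean will be wrong.

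**What to change.** **SAP 7.8.1.** Keep the descriptive table and add one supplementary analysis:
- Treated arm, Primary Efficacy Set, LOA-imputed data.
- MMRM with visit, Baseline 6MWT and Baseline by visit. Report Week 96 change with 95% CI, with no between-arm difference or p-value, so SAP 8.1 is respected.
- Unstructured covariance (6 visits, 6 × 7/2 = 21 parameters), with the protocol's heterogeneous AR(1) as the fallback on non-convergence.
- Fit the untreated arm separately if at all, because SAP 8.1 cites population differences and a joint fit would share one covariance. Leave it descriptive if too few patients remain.
- Show n per visit as walked, LOA-imputed and missing.
- State that the estimate relies on MAR. A delta analysis is optional: shift = delta × fraction missing, so delta of ±20, 40 or 60 m moves the mean by 6, 12 or 18 m at 30% missing.

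**SAP 6.6.** State that early-termination walks are assigned by study day and count as Week 96 only within 2 weeks of it. Keep the others for the model, at the nearest scheduled visit or by actual time; do not discard them. If the nearest-visit option is chosen, say what happens when that visit already has a walk, or when it is Week 96 but outside the window (for example, a walk at Week 90).

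**SAP 8.1.** State why the treated-arm estimate was dropped, or record that it is restored.

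**Cost.** One more table and some SAP wording; no new data. Imputed zeros strain the normality assumption, and protection holds only under MAR.

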7.8.2 Analyses of Secondary Efficacy Endpoints

Ability to Rise Independently from the Floor

The number and percentage of patients who are able to rise from the floor independently will be summarized by treatment group for each visit.

Time to Loss of to Rise Independently from the Floor

Time to permanent loss of ability to rise independently will be summarized. The number of patients who lost the ability, and the number of patients censored will be presented by treatment group. The percentages of patients remaining able to rise from the floor independently at 12, 24, 36, 48, 72, and 96 weeks, as estimated using the KM method, will be presented by treatment group.

The time to permanent loss of the ability to rise independently will be plotted by treatment group using the KM method, with the percentage of patients remaining able to rise being the vertical axis and time on study in weeks being the x-axis. The plot will include the number of patients at risk for each treatment group over time. The median times to loss of the ability to rise and associated 95% confidence intervals will be estimated using KM method.

Loss of Ambulation (LOA)

Time to LOA will be summarized by treatment group. The number of patients who lost ambulation, and the number of patients censored will be presented by treatment group. The percentages of patients remaining ambulatory at 12, 24, 36, 48, 72, and 96 weeks, as estimated using the KM method, will be presented by treatment group.

The time to LOA will also be plotted by each treatment group using the KM method, with the percentage of patients remaining ambulatory being the vertical axis and time on study in weeks being the x-axis. The plot will include the number of patients at risk for each treatment group over time. The median times to LOA and associated 95% confidence intervals will be estimated using KM method.

A data listing of time to LOA will be presented, which will include the censoring information.

Change from Baseline in FVC Percent Predicted

FVC% predicted is one of the three most important parameters gained from the pulmonary function tests. Observed FVC % predicted and change from Baseline will be summarized by treatment group and visit using descriptive statistics. A plot of the mean (+/- SE) of change from baseline in FVC % predicted will be generated.

Change from Baseline in NSAA Total Score

Observed NSAA total score and change from Baseline will be summarized by treatment group and visit using descriptive statistics. A plot of the mean (+/- SE) of change from baseline in NSAA total score will be generated.

CCI

7.8.4 Muscle Biopsy Endpoints

Quantity of Dystrophin Protein Expression as Measured by Western Blot

For each time point, 2 blocks of tissues will be analyzed by Western blot, each with two replicates of gels to determine the dystrophin level (% normal). The block average value from two replicate gels will be computed. The overall average is calculated as the mean of the block average values. The overall average values will be used for all analyses. In the case of only 1 available gel for a block, then that value will be used as the block average value.

For the calculation of average assay value, if there are assay results below the lower limit of detection or the lower limit of quantification, different imputation methods will be used ([Table 1](#)). The limit of detection (LOD) is 0.05 (% normal), lower limit of quantification (LLOQ) is 0.25 (% normal). Values less than LLOQ will be imputed using 1 of 4 methods: as lower bound (0 or 0.05), as upper bound (0.04 or 0.24, middle value (0.02 or 0.15) and as the actual measured value. Of them, the main analysis will be based on the actual measured value. Analyses based on other imputation methods will be considered sensitivity analyses. Samples with values above the upper limit of quantitation (8.0% normal) will not be imputed. Samples will be diluted in order to generate a number

within the measuring range. The as-measured value, adjusted for dilution factor, will be reported.

Table 1: Imputation Method for Values Outside of the Limits for Western blot

[figure not shown]
Imputation type	Treat value < LLOQ as	Analysis type
1	As measured	Main analysis
2	Using lower bound for imputation 0 ~ <LOD as 0	Sensitivity analysis
	LOD ~ <LLOQ as 0.05	
3	Using upper bound for imputation 0 ~ <LOD as 0.04	Sensitivity analysis
	LOD ~ <LLOQ as 0.24	
4	Using middle value for imputation 0 ~ <LOD as 0.02	Sensitivity analysis
	LOD ~ <LLOQ as 0.15	

LOD=limit of detection; LLOQ=lower limit of quantification

Dystrophin level (% normal) determined by Western blot will be summarized by visit. In addition, change from baseline and the fold change over baseline by visit will be summarized. Statistical summaries of observed values and change from baseline by visit will be presented in plots. A one-sample permutation test will be used to test the null hypothesis that the mean change from baseline in dystrophin level is 0 at each visit. Additionally, the by-visit analyses will be repeated pooling all post-baseline results together. A waterfall plot will be used to present each individual patient's data on the Western blot. Vertical bars are drawn for each patient, either above or below the baseline. The vertical (y) axis is the change from baseline by visit in dystrophin protein level determined by Western blot. The x-axis is the rank of the change from baseline. The waterfall plot is ordered from the worst value (lowest) on the left side to the best value (highest) on the right side. Additionally, box plots of change from Baseline will be presented by Baseline 6MWT Group (< 370 meters \geq 370 to \leq 450 meters, $>$ 450 meters), Baseline Age Group (< 9 years, \geq 9 year), previous drisapersen exposure (Yes, No) and genetic mutation type(exon 45-50, 48-50, 49-50, 50, other)

- Dystrophin level (% normal) for each gel and the average value at baseline and post-baseline: values at the gel level outside of the limits of quantification will be flagged.
- Change from baseline at post-baseline visit
- Fold change from baseline at post-baseline visit

[figure not shown]
CCI

CCI

[figure not shown]
CCI

CCI

CCI

7.9. Safety Analyses

Analyses of safety data will include AEs, SAEs, AESIs, laboratory data, ECG and ECHO measurements, vital signs, and physical examinations.

Analysis of safety data will be based on the Safety Set.

Safety analyses will be descriptive in nature. All summaries will be by treatment group for the Safety Set.

Selected safety summaries and/or listings will be presented for the subset of patients with prior exposure to drisapersen. These will include:

- Overall Summary of Adverse Events

- Summary of Treatment-Emergent Adverse Events by SOC and PT

7.9.1 Adverse Events

Adverse events will be coded using Medical Dictionary for Regulatory Activities (MedDRA Version 17.1 or higher). This coding system provides five levels to classify AEs. In general, AEs will be presented by system organ class (SOC) and PT but other classifications may be used if warranted.

The sorting order for the AE incidence tables, unless otherwise specified, will be by decreasing frequency in the active treatment arm. Multiple occurrences of the same AE (at the PT level) in the same patient will be counted only once in the frequency tables. If a patient experiences multiple episodes of the same event with different relationship/severity, the event with the strongest relationship or maximum severity to investigational drug product will be used to summarize AEs by relationship and severity. For example, for the table of AEs by SOC and PTs sorted by decreasing frequency presented by treatment group, SOC will be presented in decreasing frequency order of the active treatment column, and within each SOC, PTs will be presented in decreasing order of active treatment column. A patient is counted only once within each SOC and PT.

If a patient experiences multiple events that map to a single PT, the maximal severity grade and strongest investigator assessment of relation to study medication will be assigned to the PT for the appropriate summaries. Should an event have a missing severity or relationship, it will be classified as having a severity of “SEVERE” and/or a “DEFINITELY RELATED” relationship to study medication.

An overall summary of AEs table will be presented which will include:

- Number of Treatment-emergent AEs (TEAEs)
- Number of TEAEs by Severity
- Number of patients with at least 1 TEAE
- Number of patients with at least 1 Severe TEAE
- Number of patients with at least 1 treatment-related TEAE
- Number of patients with at least 1 treatment-emergent SAE
- Number of patients with at least 1 treatment-related, treatment-emergent SAE
- Number of patients with at least 1 TEAE leading to discontinuation of study drug
- Number of patients with a TEAE leading to death

Treatment-Emergent AEs (TEAEs)

The following TEAEs summary tables will be presented by treatment group:

- TEAEs by SOC and PT
- TEAEs by SOC, PT, and severity

- TEAEs by descending frequency of PT
- Treatment-related TEAEs by SOC and PT
- Treatment-related TEAEs by SOC, PT, and severity
- Treatment-related TEAEs by descending frequency of PT
- TEAEs reported in $\geq 10\%$ of patients in any treatment group (upon examination of the actual data, different cut-off points may be used to examine the incidence of these AEs if it is deemed appropriate)
- TEAEs reported in $\geq 2\%$ of patients in the active treatment group (and greater than untreated group)

The following listings will be produced:

- Listing of non-TEAEs
- Listing of TEAEs
- Listing of TEAEs leading to discontinuation of study drug
- Listing of TEAEs leading to withdrawal from study

Listings will include all data with an indicator for treatment period for each record when the event occurred.

Serious Adverse Events and Deaths

The following summary tables will be produced:

- treatment-emergent nonserious AEs
- treatment-emergent SAEs
- treatment-related, treatment-emergent SAEs
- deaths and AEs resulting in death
- AEs leading to study drug discontinuation by SOC and PT

The following listings will be produced:

- Listing of all AEs
- Listing of AEs leading to discontinuation
- Listing of SAEs (including pre-dosing SAEs)
- Listing of death
- Listing of SAEs that occurred prior to the initiation of study drug or after 28 days post-last dose will be excluded from the tables but will be included in the listing at the start date/time of the AE.
- Listing of AEs related to study procedure by SOC and PT

Listings will include all data with an indicator for treatment period for each record when the event occurred.

A summary of deaths and reasons for deaths will be presented by Analysis period and treatment group. A patient-level listing will be provided.

Adverse Events of Special Interest

Summaries of AEs of special interest will be summarized by SOC and PT. All standardised MedDRA Queries ([SMQs]) listed below will include broad and narrow terms. The AESI are:

- hypersensitivity (hypersensitivity SMQ)
- renal toxicity (acute renal failure SMQ)
- infusion-related reaction (IRR) (AEs occurring within 24 hours of the start of any infusion [including events occurring on the same date as an infusion where infusion start time or AE onset time was not reported])

Prior to statistical analysis, for all IRRs as defined above, IRRs will be medically reviewed by a pharmacovigilance physician. All IRRs as defined above that are considered as related to study drug by investigators will be counted in the list of medically reviewed IRRs. In addition, all IRRs as defined above that meet the following criteria will be excluded from the list of medically reviewed IRRs:

- AE was an infusion site, application site, or other local AE not associated with IRR
- AE had a clear alternate etiology that could be ascertained based on the reported event (eg, reaction to plaster, assessed as related to procedure or underlying disease by investigator)
- AE not associated with an IRR due to the nature of the event

Summaries of all medically reviewed IRRs and medically reviewed IRRs with event start time reported be generated separately. In addition, a summary table will be generated and include the following:

- Number of patients with medically reviewed IRRs
- Number of medically reviewed IRRs
- Number of medically reviewed IRRs with event start time reported
- Number of events on any day for medically reviewed IRRs

A corresponding listing will be generated for each table. Additionally, a table and listing corresponding to the AESIs that were related to study drug and/or moderate or severe will be produced. An overall summary of AESI events will include total number of events, number of SAEs, number of treatment-related events, number of unrelated events, number of mild events, number of moderate events, number of severe events, and number of events occurring on the same day as an infusion (within 24 hours or on the same day

with no time). A listing of each AESI category and a listing of AEs related to study drug for each AESI strategy will be generated.

Additional AEs for Review

Additional AEs for review will be summarized by SOC and PT All SMQs listed below will include broad and narrow terms. The AEs for additional review are:

- Drug-induced hepatotoxicities (cholestasis and jaundice of hepatic origin SMQ, hepatic failure, fibrosis, cirrhosis, and other liver damage-related conditions SMQ, hepatitis, noninfectious SMQ, liver neoplasms, benign [including cysts and polyps] SMQ, liver malignant tumors SMQ, liver tumors of unspecified malignancy SMQ, liver-related investigations, signs and symptoms SMQ, liver-related coagulation and bleeding disturbances SMQ)
- Cardiac events (cardiomyopathy SMQ, cardiac failure SMQ, and arrhythmia related investigations, sign and symptoms SMQ)
- Coagulopathy (Hemorrhage terms [excluding lab terms] SMQ, Hematopoietic thrombocytopenia SMQ, and PTs in the Embolism and thrombosis High Level Group Terms)
- Leukopenia/Neutropenia/Haematologic toxicity (Hematopoietic leukopenia SMQ)

An overall summary of additional AE for review will include total number of events, number of SAEs, number of treatment-related events, number of unrelated events, number of mild events, number of moderate events, number of severe events, and number of events occurring on the same day as an infusion.

A corresponding listing will be generated for each table. Additionally, a table and listing corresponding to the additional AEs for review that were related to study drug and/or moderate or severe will be produced.

